**Data collection:** During CNC/clinic visits (baseline, days 30, 60, 90, 120, 150 and 180) as described above, each child will have weight, length mid arm circumference and head circumference measured in duplicate. These measurements will be done by a trained member of the study staff at each center. The individual at each site will be trained to perform these

measurements according to standard methods previously described. Institutional scales, length boards and measuring tapes will be used at each center.

**Expected results:** We expect that SBS children on enteral GLN supplementation will have more rapid growth as measured by the parameters above. The group with no BSI or decreased BSI (2 episodes) during the study period is expected to have a greater increase in growth parameters compared to the group with > 2 BSI.

**Hypothesis 3:** The gut luminal microbiome is altered in pediatric SBS versus non-SBS controls, correlates with BSI and is altered by enteral GLN supplementation.

**Specific Aim 3:** To comprehensively assess the gut luminal microbiome (using state-of-the art molecular methods) in Aim 1 SBS patients versus non-SBS, age-matched control subjects (primary endpoint), to correlate major bacterial dynamics present in the lumen with BSI due to specific microbes and to explore whether the gut luminal microbiome is altered by enteral GLN treatment.

**Primary outcome:** Increased *K. pneumonia* and *E. faecalis* in the gut microbiome of SBS infants with BSI.

**Secondary outcome:** Alteration in other commensals in the gut luminal microbiome of SBS infants.

**Subjects:** Infants recruited in specific aim 1 (n=48 – subjects- 36; controls- 12) Healthy age matched infants (n=12) will be recruited from the Gastroenterology and surgery clinics.

**Sample Procurement:** Stool samples (~500 mcg), will be obtained from infants' diapers or ostomy bags. Stool specimens will be collected prospectively during visits at baseline, days 30, 60, 90, 120, 150 and 180. **Stool will also be collected whenever the patient has a BSI.**

The controls (12 healthy infants) will have serial stools collected on 4 occasions, each separated by 60 days (baseline, days 60, 120 and 180).

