### **XIII. Statistical Analysis Plan**

To assess the comparability of the two treatment groups, demographic and baseline data will be summarized for each treatment group. For continuous data, mean, standard deviation, median, min, max, first quartile and third quartile will be presented. Comparisons will be made using the two-independent sample t-test or the Wilcoxon Rank sum test, depending on the distribution of the variable. For categorical data, frequencies and percentages in each group will be presented. Comparisons will be made using Fisher's exact test. These tests will be conducted at the two-sided, 5% level of significance. In addition, demographic and baseline data for the control group will be summarized and presented as described above. The statistical analysis plan for each aim is presented below.

**Aim 1 Hypothesis:** Enteral GLN supplementation in infants with SBS after massive bowel resection for NEC will decrease BSI, and thereby decrease systemic proinflammatory cytokine concentrations.

The primary outcome variable is the incidence of BSI during the 6 months on GLN supplementation. BSI is defined as laboratory-confirmed, culture-proven bloodstream infections that meet the Centers for Disease Control and Prevention (CDC) definition. To compare the incidence of BSI during the 6 month time period, the percent of patients with at least one BSI will be calculated in each group. Since this is a pilot study, the desire is to detect a trend in improvement of BSI with GLN supplementation. Therefore the 2 groups will be compared using the Fisher's Exact test at the one-sided 10% level of significance which will indicate a significant trend. As an additional analysis, time to first BSI will be displayed using Kaplan-Meier (K-M) curves. The log-rank test will be used to test for differences in curves between treatment groups. Patients will be censored if they exit the study prior to having their first BSI. As a further exploratory analysis, time to multiple-event analyses techniques will be used to compare groups where the multiple events represent multiple episodes of BSI within patients.

Secondary outcomes include the following and will be tested at the two-sided 5% level of significance:

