- 7) The two treatment groups will be compared using the random effects repeated measures analysis of covariance for the following parameters: length velocity, weight velocity, mid arm circumference and head circumference. Length velocity and weight velocity will be analyzed as the post baseline scores. Mid arm circumference and head circumference will be analyzed as change from baseline. The time points included in the analyses will be 30, 60, 90, 120, 150, 180 days post-baseline. If required to meet the assumptions of the analyses (normality, equal variances), appropriate transformations will be used (e.g. log). Treatment groups will be compared at each individual time point using appropriate contrasts and the error term from the repeated measures model. Covariates will include baseline value, age, gender, ostomy status, feeding type (formula, breast milk). For length velocity and weight velocity, the baseline value will be the baseline length and weight values.

To evaluate the impact of BSI on the growth parameters listed above, point biserial correlation coefficients will be constructed overall and within each treatment group and tested to determine significance.

**Aim 3 Hypothesis:** The gut luminal microbiome is altered in pediatric SBS versus non-SBS controls, correlates with BSI and is altered by *enteral* GLN supplementation.

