### **Sample size**

This is a pilot study and will provide estimates of effect sizes and variability to be used to power a future definitive study. The power of this pilot study was investigated based on the primary endpoint of BSI infection rate and the study was powered to detect a trend toward improvement in BSI rates. For this study, we defined “trend” as a significant improvement tested at the one-sided, 10% level of significance. A total of 18 patients per treatment group will be enrolled in the study. Assuming a 10% dropout rate, it is expected that 16 patients per treatment group will complete the study. A sample size of 16 patients per treatment group will provide at least 85% power to detect a trend if the true BSI rates are 75% versus 30% BSI rate at the one-sided 10% level of significance. This calculation is based on the Fisher’s exact test for two proportions.

A sample size of 16 patients per treatment group will also provide at least 80% power to detect a geometric mean ratio of 2.0 for the two treatment groups for the proinflammatory cytokines assuming a coefficient of variation of 0.7 using a two-sided, 5% level of significance test.

We anticipate applying for a follow up R01 /U01 to attract other centers that will allow a larger more definitive study regarding the use of GLN in pediatric SBS.

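### The overall BSI–growth correlation in Aim 2 is not adjusted for treatment arm, so it can show an association that comes only from glutamine; the BSI dichotomy is also not named.

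*Combined protocol and SAP*

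**What the plan says.** Specific Aim 2 (section X, Assessment of Efficacy) covers GLN's effect on growth and also the impact of BSI on growth. In section XIII (Statistical Analysis Plan, Aim 2) the treatment comparison is a repeated-measures analysis of covariance over six post-baseline visits: "Covariates will include baseline value, age, gender, ostomy status, feeding type (formula, breast milk").

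The BSI question gets one sentence: "point biserial correlation coefficients will be constructed overall and within each treatment group and tested to determine significance". It names no covariates, does not define the binary BSI variable, and does not say which visit or summary of growth is used.

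Two BSI groupings appear elsewhere:

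- **Section XIII, Aim 1 (primary analysis):** "the percent of patients with at least one BSI will be calculated in each group".
- **Section X, Aim 2, expected results:** "The group with no BSI or decreased BSI (2 episodes) during the study period" is expected to grow more "compared to the group with > 2 BSI". The lower group is read here as 0–2 episodes.

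The correlation sentence refers to neither.

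**The concern.** Hypothesis 1 is that GLN lowers BSI, and Hypothesis 2 is that GLN improves growth. If both are true, placebo infants have more BSI and poorer growth, and GLN infants the reverse. A correlation computed over all infants then turns negative through arm alone, with no link between infection and growth in any child. The plan's own hypotheses therefore create the conditions under which the overall coefficient misleads.

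Three further weaknesses affect all the coefficients:

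- One BSI indicator per child counts growth before an infection as if it followed it.
- A single correlation does not use the repeated visits.
- The covariates that the plan uses for growth in the same section are dropped.

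At stake is a false or mis-sized conclusion on a stated part of Aim 2. The Background calls the BSI–growth relationship conjectural, and the pilot is meant to supply effect sizes for a later trial. A correlation does not give a growth deficit per infection.

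**Working it through.** **Inputs from the documents.** Sample size section: 16 completers per arm, and power computed "if the true BSI rates are 75% versus 30% BSI rate at the one-sided 10% level of significance". Section XIII, Aim 1: "Secondary outcomes include the following and will be tested at the two-sided 5% level of significance". The Aim 2 sentence gives no level, so two-sided 5% is assumed for the correlation.

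**Assumptions not in the documents.** (a) The BSI count distribution: Poisson as base case, negative binomial (size k) as range, each set so that P(at least one) equals the planning rate. (b) A GLN growth effect of d = 0.5–1.0 SD. (c) One normally distributed growth summary per infant.

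**The plan's own figure.** Exact enumeration of the one-sided 10% Fisher test, 16 v 16, 75% v 30%, gives power 0.857. The stated value of at least 85% reproduces.

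**Check on the count model.** The Background cites 7.8 catheter-sepsis episodes per 1000 catheter days: 7.8/1000 × 180 = 1.40 episodes, and 1 − exp(−1.40) = 75%. Poisson agrees with the placebo planning rate.

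**Poisson rates.** GLN: λ = −ln(0.70) = 0.357. Placebo: λ = −ln(0.25) = 1.386. P(more than 2) is 0.0058 and 0.163, or 0.09 and 2.6 infants of 16.

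**Overall coefficient when BSI has no effect on growth.** With equal arms:

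- Arm–BSI correlation: φ = [(p₁ − p₂)/2] / √[m(1 − m)], with m the mean of p₁ and p₂. At one or more BSI: 0.225/√(0.525 × 0.475) = 0.45. At more than two: 0.28.
- Arm–growth correlation: d/√(d² + 4), which is 0.243 at d = 0.5 and 0.447 at d = 1.0.
- The spurious correlation is roughly minus their product: about −0.11 to −0.20 at one or more BSI, and −0.07 to −0.13 at more than two.

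False-positive rates at nominal two-sided 5%, from 40,000 simulated trials per setting:

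| BSI cut | d = 0.5 | d = 0.8 | d = 1.0 |
|---|---|---|---|
| ≥1, overall | 9.4% | 15.4% | 20.9% |
| >2, overall | 6.2% | 8.0% | 9.4% |
| either, adjusted for arm | about 5% | about 5% | about 5% |

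At one or more BSI the within-arm tests also hold about 5%.

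**Can the GLN-arm coefficient be computed?** It is undefined if all 16 infants fall on one side of the cut, with probability (1 − q)¹⁶ + q¹⁶.

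- At one or more BSI, q = 0.30: 0.3%. (Placebo, q = 0.75: 1.0%.)
- At more than two, Poisson: (1 − 0.0058)¹⁶ = 91%.
- At more than two, overdispersed: 78% (k = 2), 65% (k = 1), 42% (k = 0.5).

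**The case against.** The strongest reply is that the plan also reports within-arm coefficients, which are free of confounding by arm, so a reader can see whether the overall association survives. That stands: the bias belongs to the overall coefficient only. It is a weak safeguard, though. With 16 infants a correlation must exceed about 0.50 in size to be significant at 5%, against 0.35 with 32, so an overall result that vanishes within arms looks much like loss of power. The within-arm coefficients also keep the timing, repeated-measures and covariate problems.

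It is also fair that BSI–growth is neither a primary nor a listed secondary outcome of Aim 2, that this is a pilot, and that the primary BSI test and its power are untouched.

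A reader might infer more than the documents support:

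- **That the GLN-arm correlation usually cannot be computed.** This treats more than two episodes as the plan's cut. That grouping is a narrative expectation in section X; the SAP's only patient-level dichotomy is at least one BSI, where the problem disappears. The 91% also needs Poisson counts and the full planned effect. With a true GLN rate of 50% it is 58%, and with no GLN effect on BSI it is 6%.
- **That frequent undefined values and the 9–21% error rate occur together.** They belong to different cuts.
- **That any-versus-none discards over half the information in the count.** The squared correlation between indicator and count is about 46% at the placebo rate, but 83% at the GLN rate.

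**Conclusion.** The point holds in a limited form. The overall coefficient is unadjusted for arm and can indicate a BSI effect on growth that is really a treatment effect. The size is about 9–21% false positives at one or more BSI, and 6–9% at more than two, against a nominal 5%. This rests on the planning rates, 16 per arm, Poisson counts, a two-sided 5% test and an assumed growth effect of 0.5–1.0 SD. With no GLN effect on growth the inflation disappears.

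Separately, the BSI dichotomy and growth summary are left open, which allows a choice after the data are seen, and whether the GLN-arm coefficient exists depends on that choice. The documents do not support saying that the coefficient generally cannot be computed. The point should be corrected before analysis; the primary endpoint is unaffected.

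**What to change.** 1. Leave the Aim 2 treatment-comparison model unchanged. BSI should not be added to it: BSI arises after randomisation and GLN is meant to change it, so conditioning on it would remove any growth benefit acting through fewer infections.
2. Replace the overall correlation with a separate secondary repeated-measures model of growth on number of BSI episodes, adjusted for arm, baseline value, age, gender, ostomy status and feeding type. Fix in advance whether episodes are cumulative, in the same visit interval or in the preceding one; the first interval has no on-study predecessor. Report the growth difference per BSI with a 95% CI, as an association, since BSI is not randomised.
3. Within-arm correlations may stay as descriptive, using the indicator for at least one BSI and a named growth summary.

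**Cost:** SAP wording and a little analysis. BSI dates and monthly measurements are already collected (section IX.H). The estimate will be imprecise: at the Poisson planning rates there are 0.357/6 = 0.06 episodes per GLN infant per interval and 1.386/6 = 0.23 per placebo infant, or about 16 × (0.357 + 1.386) = 28 episodes in all.

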**Genomic DNA Preparation:** Total genomic DNA will be prepared from specimens using a robust protocol that entails chemical and mechanical disruption of cells, which is performed in a HEPA-filtered, UV-sterilized PCR hood. Sham extractions are performed in parallel to detect contaminated reagents. **Broad-Range PCR:** DNA lysates are subjected to PCR with pan-bacterial 16S rDNA primers (27FYM+3 and 338R), yielding libraries of PCR amplicons representative of all bacteria in a specimen. Triplicate PCR reactions will be performed and amplicons pooled for each sample. To alleviate representational bias in PCR amplicon libraries, we will determine empirically the minimum number of PCR cycles required to generate the quantities of DNA required for direct sequencing by broad-range rDNA Q-PCR. **High throughput DNA Pyrosequencing:** Subject PCR amplicon libraries will be sequenced using the high-throughput Genome Sequencer™ FLX pyrosequencing platform of Roche/454 Life Sciences, Inc., available through the University of Colorado's Consortium for Comparative Genomics. Barcoded PCR primers will be used to multiplex ~200 libraries per pyrosequencer run. Approximately 5000 rRNA gene sequences will be determined for each sample library, which based on our preliminary studies will comprise a comprehensive census of the resident microbes. Additional sequences will be screened if coverage is less than 95%.

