- 8) Intestinal microbial groups (e.g., species, genera) will be correlated with the treatment or control arms of the GLN supplementation trial and with bacteria identified during any diagnosed BSI. The frequency of rRNA sequences will be interpreted as the relative abundances of organisms in samples of stool and standardized by gram of stool weight. Bacteria present in specimens will be preliminarily identified by use of the Naïve Bayesian Classifier Tool of the Ribosomal Database Project. The strength of association of individual microbial groups with treatment arms and/or main outcome measures will be measured by comparing the abundances of these groups using the non-parametric Kruskal-Wallis test. Experimental reproducibility and inter- and intra-individual similarities in microbial populations will be assessed by calculating and comparing the sequence-abundance-based Morisita-Horn index. In all statistical analyses 2-sided *p*-values less than 0.05 will be considered statistically significant. Results will be corroborated through the phylogeny-based UniFrac metric, which assesses population-wide differences in microbial lineages between different groups of subjects (SBS vs. control). Stool-associated bacteria collected at BSI incidence will be compared to the species identified on blood culture to determine whether intestinal bacteria are potential sources for BSI. Alternatively, absence of particular species from the stool at the time of BSI diagnosis will indicate that lack of specific bacterial species from the stool predisposes to BSI. Tissue samples collected during endoscopy or surgery and intestinal fluid aspirated during endoscopy will be analyzed in parallel with stool samples in order to assess the use of stool samples as proxies for intestinal samples. Patterns will also be reviewed to assess for relationships to enteral feeding rate.

These methods have been used and demonstrated in 2 published studies by one of the collaborators/co-investigators.

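### Aim 3 standardizes read proportions by stool weight, which makes a mass-free quantity depend on the amount of stool taken and biases per-taxon tests if sample weights differ systematically between groups

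*Combined protocol and SAP*

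**What the plan says.** Section XIII, Aim 3, item 8 defines the analysis variable: sequence frequencies are to be "interpreted as the relative abundances of organisms in samples of stool and standardized by gram of stool weight". It gives no formula. The association of individual microbial groups with treatment arm or main outcome measures is then tested by "comparing the abundances of these groups using the non-parametric Kruskal-Wallis test", and two-sided p-"values less than 0.05 will be considered statistically significant".

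Section X, High throughput DNA Pyrosequencing, sets the depth: "Approximately 5000 rRNA gene sequences will be determined for each sample library". More sequences are added only if coverage falls below 95%; stool mass plays no part. The same section names quantitative PCR, but only to find the "minimum number of PCR cycles required to generate the quantities of DNA required for direct sequencing by broad-range rDNA Q-PCR".

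Section X, Sample Procurement, gives one nominal amount for all stool ("Stool samples (~500 mcg"), taken from infants' "diapers or ostomy bags". It states no tolerance and no wet or dry basis. Neither the procedures nor the data collection section says that sample weights will be recorded.

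**The concern.** A per-gram scale makes sense for an amount, such as 16S copies. It does not make sense for a share of a fixed number of reads. The reads from one library sum to 1 as proportions; after division by weight w they sum to 1/w. Every taxon then looks more abundant in a lighter sample, although composition is unchanged.

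The variable feeds the per-taxon tests. These bear on the SBS versus control comparison, which Section X labels the Aim 3 primary endpoint, and on the Aim 3 primary outcome of two named species in SBS infants with BSI. If the compared groups supply different masses of stool, a difference in sampling would be reported as a difference in the microbiome.

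**Working it through.** The documents state no figure for this point, so there is none to reproduce.

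**Unit check.** Take 500 reads of 5000 for one taxon: 500/5000 = 0.10, whatever the stool weight. Divided by 0.25 weight units this is 0.40; divided by 0.50 it is 0.20. That is a 2-fold difference from identical composition.

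**Inputs from the documents.** 36 SBS infants and 12 controls (Section X, Subjects), the Kruskal-Wallis test and two-sided 0.05 (Section XIII, item 8).

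**Assumed inputs.** One sample per infant, the same true abundance distribution in both groups, between-infant SD of ln abundance 0.5, 1 or 1.5, within-group SD of ln weight 0.3, and a between-group weight ratio of 1 to 3.

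**Approximation.** On the log scale, division by weight shifts one group by ln(ratio), and the SD becomes √(SD_abundance² + SD_weight²). With SE factor √(1/36 + 1/12) = 0.333 and rank-test efficiency 3/π,

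z = ln(ratio) / √(SD_abundance² + 0.3²) / 0.333 × √(3/π), and P(false positive) ≈ Φ(z − 1.96).

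For ratio 2 and SD 1: √(1 + 0.09) = 1.044; 0.693/1.044 = 0.664; 0.664/0.333 × 0.977 = 1.95; Φ(−0.01) ≈ 0.49. Simulation gives 47%, so formula and simulation agree.

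**Simulated false-positive rates, 36 v 12, at abundance SD 0.5 / 1 / 1.5:**

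| Weight ratio | Proportion divided by weight |
|---|---|
| 1 (weights vary, same distribution) | about 5% throughout |
| 1.5 | 49% / 19% / 11% |
| 2 | 92% / 47% / 27% |
| 3 | 100% / 84% / 52% |

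Repeat runs move these by one or two points, hence the rounded ranges of about 10-50%, 25-93% and 52-100%.

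**Second model.** This used binomial sampling of 5000 reads, median abundance 10%, logit SD 0.5 / 1 / 2 and weight CV 0.3. A ratio of 1.25 gives 22% / 10% / 7%, and a ratio of 2 gives 96% / 57% / 22%. With equal mean weights the rate stays at 4.3-5.4%, even at CV 0.7. The undivided proportion gives 4.0-5.9% in every setting, including the 18 v 18 and 16 v 16 comparisons.

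**Cost of noise alone.** For a true 2.5-fold difference (SD 1, 36 v 12), simulated power is 73% on the plain proportion. It falls to 70% with ln-weight SD 0.3 and to 57% with SD 0.7. A 2-fold weight imbalance opposing the effect (ln-weight SD 0.3) cuts it to 10%.

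**The case against.** The best defence is that dividing by grams is only one reading. The clause may mean that a standard mass of stool enters the extraction, which would be harmless. The SAP also says its methods were used in two published studies, where the meaning may be clear. This stands in part: no formula is given, and the intent cannot be settled from the documents. But in the sentence as written the thing standardized is the sequence frequency, not the extraction input, so the literal rule is the wrong one and needs correcting either way.

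The defence also limits the reach of the point. A reader might infer several things that the documents do not support:

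- **That any variation in weight creates false differences.** It does not. Weights with the same distribution in both groups leave the error rate near 5%.
- **That group weights are known to differ.** They are not. One nominal amount applies to all stool, and home and clinic samples alike can be portioned. A systematic difference is plausible, because controls have no resection and so ostomy samples come from SBS infants, collection arrangements differ, and BSI samples are unscheduled. No weights are given to show it.
- **That every Kruskal-Wallis comparison is biased.** GLN and placebo are randomized, so no systematic difference is expected unless treatment alters the stool.
- **That all of Aim 3 is affected.** A factor common to all taxa in a sample cancels from Morisita-Horn and UniFrac computed on within-sample proportions, and it leaves presence or absence unchanged. UniFrac is community-wide, however, and cannot verify a result for a single taxon.

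**Conclusion.** The rule is wrong as written and should be changed. It makes a proportion from a fixed read depth depend on sample mass, with no measured bacterial load to justify a per-gram scale. The certain consequence, if weights vary and the rule is followed, is added noise. Bias in the per-taxon tests is conditional on weights that differ systematically between the compared groups. It would then run in the same direction for all taxa, at about 10-50%, 25-93% and 52-100% false positives for 1.5-, 2- and 3-fold ratios.

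Those sizes rest on assumed spreads and assumed ratios. They show sensitivity and do not forecast this trial. The BSI primary endpoint of the trial is not touched.

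**What to change.** In Section XIII, Aim 3, item 8, delete the clause on stool weight and state that the analysis variable is the proportion of reads per library. If the clause was meant to describe a fixed stool mass entering DNA extraction, move it to Genomic DNA Preparation in Section X and give the mass there. Either change is one sentence and costs nothing. It also gives stool, duodenal fluid and biopsy samples one common scale, which a stool-weight rule cannot do.

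An amount per gram should appear only as a separate, optional analysis: relative abundance × measured 16S copies per gram. A reader might take the Q-PCR already named as supplying this, but it only sets the cycle number. The option needs calibrated quantification and recorded sample weights, neither of which is now planned, so it is not free.

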4. The family will be instructed on how to administer GLN and placebo. During the baseline visit, the initial teaching will be done and they will be provided with the premeasured powder. The dose (0.6g/kg/d (0.3g/kg/dose) of GLN or ALA) will be measured out in the research pharmacy based on the weight of the child at the visit into individual packets. Children hospitalized during the study will receive GLN or ALA from the research pharmacy delivered to the patient's bedside to be administered by nursing staff. At subsequent visits (except visit on day 180), this teaching will be repeated as the dose to be administered will change based on the weight of the child. The family will also be given a weekly drug diary to complete in between visits. They will return the drug diary to the study staff during subsequent visits.
5. During the initial visit, stool will be collected into sterile containers and stored at -80°F until analysis for sIgA and bacterial composition evaluation. It is anticipated that the majority of stool will be collected in clinic during the study visit. If stool is collected in clinic, the stool will be stored immediately in the -80°F freezer without any need for DNA stabilizer.

If stool is not collected during this visit, families will be instructed on how to collect stool for evaluation into a sterile container. They will put this in a storage bag and kept cold until picked up by the home health team or delivered to the research team.

Patients already enrolled will be provided with a sterile container with instructions to collect stool and bring in to the clinic visit for storage and analysis. The family will be asked to collect stool 24-48 hours before their clinic visit and put the stool in a sterile container which will be supplied to them by the study team. They will put this in a storage bag and keep cold. They will bring the sample to the clinic visit. RNAlater may be used with samples when samples are unable to be obtained within 24 hours of the clinic visit.

**Stool sIgA analysis:** sIgA will be determined by ELISA as described.

**During baseline visit and visit on day 180** the following additional procedures will be done: Extra 2 ml of blood will be collected for plasma glutamine, proinflammatory cytokines analysis, flagellin and LPS specific IgG levels.

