- 1) Plasma proinflammatory cytokine levels: TNF- $\alpha$ , IL1- $\beta$ , IL-6, and IL-8. Change from baseline values at 180 days will be computed for cytokine levels. Change from baseline to 180 days values will also be calculated for the flagellin and LPS IgG levels. Appropriate transformations of the data (e.g. log) will be done prior to calculating change from baseline in order to meet the assumptions of the analyses (i.e. normality, equal variance). Analysis of covariance techniques will be used to compare the change from baseline scores of the treatment groups. Covariates included in the analysis will be baseline value, age, gender, ostomy status, feeding type (formula, breast milk).
- 2) Length of hospital stay and number of readmissions: For length of hospital stay, treatment groups will be compared using the Wilcoxon Rank Sum test. For number of readmissions, either a Wilcoxon Rank Sum test or a Chi-Square test for homogeneity will be used to compare groups, depending on the variability of the number of readmissions.
- 3) Stool sIgA levels: Treatment groups will be compared using the random effects repeated measures analysis of covariance. The response variables for each of the parameters will be change from baseline. The time points included in the analyses will be 30, 60, 90, 120, 150, 180 days post-baseline. If required to meet the assumptions of the analyses (normality, equal variances), appropriate transformations will be used. Treatment groups will be compared at each individual time point using appropriate contrasts and the error term from the repeated measures model. Covariates will include baseline value, age, gender, ostomy status, feeding type (formula, breast milk).
- 4) Proportion of nutrition delivered enterally versus parenterally: The statistically analysis approach for this endpoint will be the same as for the Stool sIgA levels discussed above. Transformations appropriate for proportions may be used, if necessary, to meet assumptions of the analyses.
- 5) Plasma glutamine: The statistical analysis approach for this endpoint will be the same as for the proinflammatory cytokine levels discussed above.
- 6) Impact of level of compliance on outcome will be evaluated for a dose effect analysis.

**Aim 2 Hypothesis:** Enteral GLN supplementation will improve somatic growth parameters in Aim 1 patients.

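### The exploratory glutamine-versus-placebo microbiome test makes no use of the day-0 stool: it is valid, but it gives up power and cannot separate a chance baseline imbalance from a treatment effect

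*Combined protocol and SAP*

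**What the plan says.** In XIII. Statistical Analysis Plan, Aim 3 (item 8), microbial groups "will be correlated with the treatment or control arms of the GLN supplementation trial". The strength of association of each group with treatment arm "will be measured by comparing the abundances of these groups using the non-parametric Kruskal-Wallis test", and two-sided p-"values less than 0.05 will be considered statistically significant". No baseline value, covariate or follow-up time point is named for this test.

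The baseline measurement exists. Study Procedures, item 5, states: "During the initial visit, stool will be collected into sterile containers". X. Assessment of Efficacy, Specific Aim 3, gives the full schedule: "Stool specimens will be collected prospectively during visits at baseline, days 30, 60, 90, 120, 150 and 180". The same section words the arm contrast as exploratory: the aim is "to explore whether the gut luminal microbiome is altered by enteral GLN treatment".

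Elsewhere the SAP uses baseline. Stool sIgA, which comes from the same scheduled collections, is analysed as change from baseline, and "Covariates will include baseline value, age, gender, ostomy status, feeding type". The enteral proportion follows the sIgA approach. Cytokines and plasma glutamine are compared by analysis of covariance with the baseline value as a covariate. The growth models also carry a baseline value.

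**The concern.** Whether glutamine alters the microbiome is a question about change from where each infant started. In an arm comparison of follow-up abundances alone, stable differences between infants stay in the error term. A taxon that was unequal between arms at day 0 will also tend to be unequal later. With 16 to 18 infants per arm and many taxa, some chance imbalances are likely.

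Two things are at stake: power to see a real change in a taxon, and the ability to read an individual positive result. Both bear on the pilot's stated use, which is to supply effect sizes and variability for a definitive study.

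**Working it through.** **Inputs from the documents.** 1:1 randomisation; 18 infants enrolled and 16 expected to complete per arm; two-sided 5% for Aim 3; one baseline and six scheduled post-baseline stools per infant.

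**Inputs assumed.** The correlation rho between baseline and follow-up abundance (0, 0.3, 0.5, 0.7); a treatment effect of 0.8 SD; one follow-up value per infant; abundance normally distributed on some monotone scale. The documents give none of these.

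**The plan's own figures.** The SAP gives no power for the microbiome contrast. Its power for the primary endpoint does reproduce. Exact enumeration of Fisher's test with 16 per arm, 75% versus 30%, one-sided 10%, gives 85.7%, against a stated minimum of 85%. The sample size also agrees: 16/(1 − 0.10) = 17.8, rounded up to 18.

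**1. How often a taxon is imbalanced at day 0.** In SD units the difference in baseline means has standard error √(2/n).
- n = 16: √(2/16) = 0.354; 0.5/0.354 = 1.41; P(|Z| > 1.41) = 15.7%.
- n = 18: √(2/18) = 0.333; 0.5/0.333 = 1.50; P(|Z| > 1.50) = 13.4%.

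These are frequencies of imbalance, not error rates.

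**2. Type I error with no true effect** (simulation, 40,000 trials per setting, 16 per arm). Kruskal-Wallis on follow-up alone rejects in 4.6% to 4.7% of trials at every rho. Overall error is therefore intact.

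The picture differs among trials in which the taxon happened to be imbalanced by 0.60 to 0.85 SD at day 0:

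| rho | Kruskal-Wallis | Rank ANCOVA |
|---|---|---|
| 0.3 | 6.4% | 5.1% |
| 0.5 | 11.1% | 4.8% |
| 0.7 | 18.6% | 6.0% |

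**3. Power for a 0.8 SD effect, 16 per arm, two-sided 5%** (simulation; repeat runs differ by about one point):

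| rho | Kruskal-Wallis | Quade rank ANCOVA | Gain (points) |
|---|---|---|---|
| 0 | 56% | 56% | 0 |
| 0.3 | 56% | 59% | 3 |
| 0.5 | 56% | 67% | 11 |
| 0.7 | 56% | 81% | 25 |

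**4. The same in infants.** Adjustment multiplies the residual variance by 1 − rho². To match 16 adjusted infants per arm, an unadjusted analysis needs 16/(1 − rho²):
- rho 0.3: 16/0.91 = 17.6
- rho 0.5: 16/0.75 = 21.3
- rho 0.7: 16/0.51 = 31.4

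**5. Why a plain change score is not the remedy.** Its variance is 2(1 − rho) relative to follow-up alone. That is 1.4 at rho 0.3, 1.0 at 0.5 and 0.6 at 0.7, so below 0.5 it is worse than not adjusting. The only continuous effect in the plan, given for cytokines, is a geometric mean ratio of 2.0 with a coefficient of variation of 0.7. This corresponds to ln 2/√ln(1 + 0.49) = 0.693/0.631 = 1.10 SD. At that effect and rho 0.3, simulated power is 68% for Kruskal-Wallis on change, 83% on follow-up alone and 85% for rank ANCOVA.

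**The case against.** The best defence is that an unadjusted rank test in a randomised comparison is valid. That stands. A reader might infer from the missing baseline term that false positives are inflated. The documents do not support this: allocation is randomised 1:1, and the check above finds overall error just under 5% at every correlation. The excess arises only given an imbalance.

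The contrast is also exploratory, in a pilot not powered on any taxon, and Aim 3's primary endpoint compares infants with short bowel syndrome with controls. That limits the weight of the point. It does not justify leaving collected data unused when the change is one of wording.

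The gain depends on a correlation that the documents do not give. These are infants of at most 12 months whose feeds are advanced during follow-up, so a low correlation between day 0 and day 180 is plausible, and at zero nothing is gained. Many taxa may be undetectable in many stools. If a taxon is found in only 30% of samples (assumed), the simulated gain is about 1, 5 and 13 points at correlations 0.3, 0.5 and 0.7. Both points stand as limits on size.

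Finally, the plan does not disregard baseline stool altogether. In Aim 3, "inter- and intra-individual similarities in microbial populations will be assessed by calculating and comparing" the Morisita-Horn index, and the SAP compares baseline data between arms. Neither closes the gap. The index is not tied to the arm contrast, UniFrac is specified for short bowel syndrome versus control, and stool taxa are not named among the baseline data.

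**Conclusion.** The point holds as one of efficiency and interpretability. The exploratory glutamine-versus-placebo contrast is tested without the baseline stool that the protocol schedules, although the SAP uses baseline for sIgA from the same collections. The test keeps its overall size. It cannot separate a chance day-0 imbalance from a glutamine effect, and an imbalance of at least 0.5 SD occurs for any one taxon in about 16% of trials with 16 per arm (13% with 18).

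The power forgone for a 0.8 SD effect runs from nothing at a correlation of 0 to about 25 points at 0.7. This rests on the assumed effect, the assumed correlations and normally distributed abundance. The absence of a baseline term is certain; the size of the loss is not.

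A reader might also infer that all seven scheduled stools per infant are to be pooled as independent observations. The SAP does not say so; it is silent on which stools enter the test. That is a separate gap, but it must be settled before any adjusted analysis can be run. Comparisons with the control infants are not affected by this point.

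**What to change.** In XIII. Statistical Analysis Plan, Aim 3, item 8, for the glutamine-versus-placebo contrast only:

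- Replace Kruskal-Wallis by Quade rank ANCOVA, with the infant's day-0 abundance of that taxon as covariate. This keeps the non-parametric approach and needs no rule for taking logs of zeros.
- Name one follow-up value per infant in advance, for example the day-180 abundance or the mean of the scheduled post-baseline stools. Leave out stools triggered by a bloodstream infection.
- State a simple rule for an infant without a usable day-0 stool, for example assigning the middle baseline rank with arms pooled.
- Do not use a plain change score.
- Keep Kruskal-Wallis for comparisons that have no baseline.

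The cost is SAP wording, slightly more analysis work and the missing-baseline rule. No samples, visits or procedures are added.
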